### 5.3. Secondary efficacy endpoints

The viral activity parameters HBsAg (qualitative), HBeAg (quantitative / qualitative), Anti-HBs (quantitative / qualitative), Anti-HBe (qualitative), HBcrAg (quantitative), HBV DNA (quantitative), HBV RNA (quantitative) and derivation from these parameters (also including HBsAg [qualitative] derivations) will be assessed as secondary efficacy objectives.

### 5.2.1 Parameter Definitions

The following parameters will be derived as follows:

*Viral breakthrough during 24 weeks of treatment (all subjects), during 48 weeks of treatment (subject with treatment extension) and during NA follow up for all subject who switch to NA-treatment during follow-up:*

HBV virological breakthrough is defined as having a confirmed on-treatment HBV DNA increase by  $>1$  log10 from nadir level (lowest level reached during 24/48 weeks treatment) or a confirmed on-treatment HBV DNA level  $>200$  IU/mL in subjects who had HBV DNA level below the lower limit of quantification (LLOQ) of the HBV DNA assay.

The proportion of subjects with a viral breakthrough is defined as follows:

---

- 0 (No) = subject has not had a viral breakthrough (see definition above) up to the considered time point
- 1 (Yes) = subject has a viral breakthrough at the considered time point or has had a viral breakthrough before (regardless of the HBV DNA result at the considered time point)
- 2 (No: ongoing): subject has not had a viral breakthrough (see definition above) up to the last time point but is still ongoing (only for interim analysis)

Confirmed means that the criterion should be fulfilled at 2 or more consecutive time points or at the last observed time point on-treatment. On-treatment means in the treatment phase, except for the baseline record.

The proportion of subjects with a viral breakthrough during initial 24- or 48-weeks treatment but still on NA Treatment (Yes / No)

Note: For Viral breakthrough during NA follow up, only subject on NA treatment will be include in the denominator.

*Viral relapse* is defined in the follow-up phase as follows:

- 1 (Yes) = viral relapse: confirmed  $\geq 2000$  IU/mL quantifiable.
- 0 (No) = no viral relapse: at least one post-treatment measurement available and not a viral relapse
- 2 (Not applicable) = no post-treatment HBV DNA measurements available
- 3 (No: ongoing) = no viral relapse: at least one post-treatment measurement available and not a viral relapse but still ongoing (only for interim analysis)

Confirmed means that the criterion should be fulfilled at 2 or more consecutive time points or at the last observed time point.

Note: viral relapse will only be assessed for those subjects who at the actual end of treatment have HBV DNA  $< 20$  IU/ml detectable/ undetectable.

*Biochemical relapse* is defined in the follow-up phase as follows:

- 1 (Yes) = biochemical relapse: confirmed  $ALT > 2 * ULN$ .
- 0 (No) = no biochemical relapse: at least one post-treatment measurement available and not a viral relapse
- 2 (Not applicable) = no post-treatment ALT measurements available

---

- 3 (No: ongoing) = no biochemical relapse: at least one post-treatment measurement available and not a biochemical relapse but still ongoing (only for interim analysis)

Confirmed means that the criterion should be fulfilled at 2 or more consecutive time points or at the last observed time point.

Note: biochemical relapse will only be assessed for those subjects who at the actual end of treatment have  $ALT \leq ULN$ .

*Clinical viral relapse is defined as follow:*

- 1 (Yes) = if both viral and biochemical relapse
- 0 (No) = otherwise and not ongoing
- 2 (Not applicable) = no post-treatment measurements available
- 3 (No: ongoing) not both viral and biochemical relapse but still ongoing (only for interim analysis)

Note: clinical viral relapse will only be assessed for those subjects who at the actual end of treatment have  $HBV\ DNA < 20\ IU/ml$  detectable/ undetectable and  $ALT \leq ULN$ . *Seroconversion of HBsAg (all subjects) / HBeAg (positive subjects) at week 24 of the treatment and at week 48 of the treatment (only subjects with treatment extension)* is defined as a confirmed loss of HBsAg/HBeAg at week 24/48 of the treatment. Loss is defined as a baseline HBeAg /HBsAg (qualitative) with a "REPEAT REACTIVE, CONFIRMED" or "POSITIVE" result and a post-baseline assessment with a "NEGATIVE" result.

*Seroconversion of HBsAg (all subjects) /HBeAg (positive subjects) at week 24 of the treatment and at week 48 of the treatment (only subjects with treatment extension)* is defined as:

- Use the selected time point for the week 24 or 48 visit as described in 2.3.
- A confirmed loss of HBsAg/HBeAg at week 24/48-of the treatment (i.e. seroclearance)
- and an appearance of Anti-HBs/Anti-HBe.

Loss is defined as a baseline HBeAg /HBsAg (qualitative) with a "REPEAT REACTIVE, CONFIRMED" or "POSITIVE" result and a post-baseline assessment with a

---

"NEGATIVE" result. Appearance is defined as a baseline Anti-HBs/ Anti-HBe (qualitative) with a "NEGATIVE" result and a post-baseline assessment with a "POSITIVE" result. Both criteria should be fulfilled.

*Status changes from baseline at week 24 and at week 48 (only subjects with treatment extension)* for HBsAg, HBeAg, anti-HBs and anti-HBe status. Only the qualitative result will be considered. Use the selected time point for the week 24 or 48 visit as described in 2.3. The following categories were defined. The categories can be extended when missing values are present. A borderline result will be mapped as negative.

- Positive to Positive
- Negative to Negative
- Negative to Positive
- Positive to Negative

Maximum decrease from baseline is defined as the minimum value for change of baseline for the viral activity parameters HBeAg, HBsAg, HBVRNA, HBVDNA and HBcrAg)

*Biochemical response* or alanine aminotransferase (ALT) normalization from baseline per post-baseline time point is defined for subjects with elevated ALT (ALT>ULN) at baseline as:

- 0 (No) = ALT>ULN
- 1 (Yes) = ALT $\leq$ ULN

*On-treatment failure during week 24 period is defined as:*

- Subject who has at week 4 HBVDNA < 1log10 IU/mL decline from baseline and confirmed by retesting at week 8 visit (apply only for the naïve treatment population)
- Or for subject who experienced viral breakthrough as defined above

*On-treatment failure during week 48 period is defined as:*

- Subject whom after completed week 24 treatment and still on JNJ-56136379 experienced viral breakthrough as defined above

---

- Subject who did not meet the treatment extension criteria at week 24 as defined in the protocol (this should be derived using the criteria below)
  - Completed 24 weeks of treatment
  - HBVDNA levels < 200 IU/mL at week 20
  - No safety concerns during the initial 24 weeks of treatment
- Subject who did not meet the week 40/44 treatment completion criteria as defined in the protocol (this should be derived using the criteria below)
  - Completed 48 weeks of treatment
  - At week 40 and confirmed at week 44
    - Normal ALT levels or elevated ALT levels by investigator opinion
    - HBV DNA <LLOQ
    - HBeAg negative
    - HBsAg < 500 IU/mL
    - $\geq 1$  log10 IU/mL decline in HBsAg from baseline

*Post-treatment failure during follow-up with NA treatment is defined as:*

Subject who completed study treatment at week 24 and did not met the treatment extension criteria or subject who did not met treatment completion criteria at week 48 as defined above or subjects who discontinued study treatment earlier and experienced viral breakthrough as defined above (NA treatment)

*Post-treatment failure during follow-up free treatment is defined as:*

Subject who completed 48 weeks of treatment (treatment extension phase) and met the treatment completion criteria and experienced viral relapse as defined below

- HBV DNA <20 IU/mL at week 40/44 (requirements of the treatment completion criteria)
- Confirmed post-treatment (follow-up free treatment) increase of HBV DNA  $> 2000$  IU/mL

Response categories of the viral activity parameters will be tabulated per analysis phase and period and analysis timepoint if more than one records in the interval is available

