
 
To evaluate efficacy in terms of HBsAg (in all subjects) or HBeAg (in HBeAg-positive subjects only) seroclearance and/or seroconversion.
 
	
 
Proportion of subjects with HBsAg or HBeAg seroclearance (defined as HBsAg or HBeAg negativity, respectively, based on the assay used) during study treatment and follow-up.
 
Proportion of subjects with HBsAg or HBeAg seroconversion (defined as HBsAg or HBeAg negativity and anti-HBs or anti-HBe antibody positivity, respectively) during study treatment and follow-up.
 

 
To evaluate the frequency of subjects with biochemical response.
 
	
 
Proportion of subjects with ALT improvement and normalization during study treatment and follow-up.
 

 
To evaluate the frequency of HBV virological breakthrough.
 
	
 
Proportion of subjects with virological breakthrough during study treatment defined as confirmed on-treatment HBV DNA increase by <math>>1 \log_{10}</math> from nadir level or confirmed on-treatment HBV DNA level <math>>200</math> IU/mL in subjects who had HBV DNA level below the lower limit of quantification (LLOQ) of the HBV DNA assay.
 

 
To evaluate the potential effect of JNJ-56136379 on the pharmacokinetics of NA when coadministered.
 
	
 
Pharmacokinetics of NA when administered as monotherapy or when coadministered with JNJ-56136379.
 

Objectives	Endpoints

 
To evaluate the pharmacokinetics of JNJ-56136379 when administered as monotherapy.
 
To evaluate the potential effect of NA on the pharmacokinetics of JNJ-56136379 when coadministered.
 
To assess changes in the HBV genome sequence.
 
	
 
Pharmacokinetics of JNJ-56136379 when administered as monotherapy or when coadministered with an NA.
 
Emergence of treatment-associated mutations during study treatment and follow-up.
 

Exploratory	

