## 6.1. Treatment Duration

All subjects will be treated for at least 24 weeks, unless they discontinue treatment early. Treatment will be extended for another 24 weeks in a treatment extension phase for subjects who meet the following criteria:

- Subject completed 24 weeks of treatment
- Subject had HBV DNA levels <200 IU/mL by Week 20 of the initial 24-week treatment period
- During the initial 24 weeks of treatment the subject did not have any safety concerns that would preclude continued treatment, as determined by the investigator
- For subjects who were enrolled in the study before the Amendment 2 came into effect: subject needs to consent for participation in the extension phase.

Subjects in the JNJ-56136379 250 mg monotherapy arm (Treatment Arm 6) who meet the treatment extension criteria, will receive JNJ-56136379 in combination with NA treatment from Week 24 to Week 48.

Subjects not meeting the above criteria will be followed-up until 24 weeks after EOT. These subjects should continue or, in case of JNJ-56136379 monotherapy, start NA treatment at the end of the 24-week study treatment as per local treatment guidelines.

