## **10.2. Discontinuation of Study Treatment/Withdrawal from the Study**

### **Discontinuation of Study Treatment**

A subject will not be automatically withdrawn from the study if he or she has to discontinue study treatment before the end of the 24- or 48 week treatment phase, as applicable.

A subject's JNJ-56136379 treatment must be discontinued and NA may be discontinued based on investigator judgement in consultation with the sponsor if:

1. The subject withdraws consent.
2. The investigator believes that for safety reasons or tolerability reasons (eg, AE) it is in the best interest of the subject to discontinue study treatment.
3. The subject becomes pregnant.
4. The subject has a  $\geq$  gradea 3 rash (see [Attachment 3](#)).
5. The subject has a  $\geq$  grade 3 allergic reaction, nausea, or diarrhea.
6. The subject has a grade 4 AE or confirmed laboratory abnormality (with the exception of ALT/AST elevations) considered at least possibly related to study drugs by the investigator.
7. The subject experiences a treatment-emergent elevation of ALT  $>2x$  baseline value, in combination with either direct bilirubin  $>1.2x$  ULN or INR  $>1.5x$  ULN or serum albumin  $<$  LLN, confirmed by retesting.
8. The subject has signs of hepatic decompensation (ie, clinical evidence of ascites, bleeding varices, or hepatic encephalopathy).
9. The subject has a confirmed  $\geq$  grade 3 serum creatinine abnormality, regardless of the relationship to the study drugs. In this case, JNJ-56136379 must be discontinued. The subject may continue ETV or switch from TDF to ETV at the investigator's discretion and enter follow-up.

Subjects who are receiving TDF and develop confirmed treatment-emergent  $\geq$  grade 3 abnormalities in urinalysis, considered at least possibly related to TDF, may switch to ETV and continue JNJ-56136379 for 4-8 weeks. If the urinalysis abnormality persists at the end of the 4-8 weeks NA switching phase, JNJ-56136379 must be discontinued. Subjects may continue NA treatment at the investigator's discretion and enter follow-up.

---

a Grades in this list are per the DAIDS Toxicity Grading Scale.

If the confirmed  $\geq$  grade 3 urinalysis abnormality is not considered at least possibly related to TDF or ETV, or any other concomitant disease and its medication, JNJ-56136379 must be discontinued. Subjects may continue NA treatment at the investigator's discretion and enter follow-up.

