10. The subject has a QTcF prolongation (defined as a QTcF value of  $>500$  ms, or an increase from baseline of  $>60$  ms) at any given time point (confirmed by repeat ECG).
11. The subject has at Week 4  $<1 \log_{10}$  IU/mL decline in HBV DNA from baseline, confirmed by retesting at the Week 8 visit (treatment-naïve only).
12. The subject has confirmed HBV virological breakthrough (ie, confirmed on-treatment HBV DNA increase by  $>1 \log_{10}$  IU/mL from nadir level or confirmed on-treatment HBV DNA level  $>200$  IU/mL in subjects who had HBV DNA level  $<$  LLOQ of the HBV DNA assay).
13. The subject requires treatment with any of the disallowed medications listed in Section 8.

Retesting for confirmation of the above-mentioned abnormal safety parameters (ie, not applicable to criteria 11 and 12 listed above) should take place within 72 hours after the initial results become available and may require an unscheduled visit.

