### 5.2.1 Secondary Analysis

- Descriptive statistics of the actual values (original unit and log10 transformed values) and the change from baseline (log10 transformed values) over time for qualitative viral activity parameters according to the specification described in section 2.6 will be included.
- LS means (SE) of change from baseline (and 95% confidence interval) for qualitative viral activity parameters per time point and overall based on log10 transformed values will be analyzed by subject population and part using mixed effects model for repeated measures similar as described in section 5.2.1.1.. Also P-values for treatment, time, their interaction and overall will be added.
- LS means (SE) of change from baseline (and 95% confidence interval) for qualitative viral activity parameters (except for HBeAg) per time point and overall based on log10

---

transformed values will be analyzed by subject population, part and by HBeAg status using mixed effects model for repeated measures similar as described in section 5.2.1.1. Also P-values for treatment, time, their interaction and overall will be added.

- A tabulation of the proportion of subjects with virological breakthrough during 24 week treatment and during 48 week treatment (only subjects with treatment extension) will be included.
- A tabulation of the proportion of subjects with viral relapse will be provided. For the purpose of the analysis, the denominator will only include those subjects with values Yes and No.
- Descriptive statistics of the maximum decrease from baseline ( $\log_{10}$  transformed values) over time for qualitative viral activity parameters according to the specification described in section 2.6 will be included.
- A tabulation of the status change from baseline at week 24 and at week 48 (only subjects with treatment extension) will be displayed by viral activity parameter.
- A tabulation of the proportion of subjects who meet the criteria of response categories per time point defined in section 5.3.1 will be displayed by viral activity parameter.
- A tabulation of the proportion of subjects who meet the criteria of response categories per period defined in section 5.3.1 (additional information in the table) will be displayed by viral activity parameter.
- A tabulation of the qualitative result of HBeAg and HBsAg per timepoint (week 24 and week 48) will be included.
- A tabulation of the biochemical response per time point will be included.

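### The SAP's 48-week viral breakthrough proportion is conditional on entering the extension, and no SAP output clearly supplies the protocol's endpoint of breakthrough during study treatment

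*SAP*

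**What the plan says.** Protocol 2.1 lists as a secondary endpoint the "Proportion of subjects with virological breakthrough during study treatment defined as confirmed on-treatment HBV DNA increase by" more than 1 log10 from nadir, or above 200 IU/mL after a value below the LLOQ. It has no Week 24 cut and no restriction to extension subjects.

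SAP 5.3, Parameter Definitions, divides this into time frames: "during 24 weeks of treatment (all subjects), during 48 weeks of treatment (subject with treatment extension"), plus a separate frame for NA follow-up. The Secondary Analysis list repeats the split for the table, calling for the "proportion of subjects with virological breakthrough during 24 week treatment and during 48 week treatment (only subjects with treatment extension").

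Protocol 6.1 sets the conditions for extension. Two of them are "Subject completed 24 weeks of treatment" and "Subject had HBV DNA levels <200 IU/mL by Week 20 of the initial 24-week treatment period". Protocol 10.2 says "A subject's JNJ-56136379 treatment must be discontinued and NA may be discontinued based on investigator judgement" if, among other criteria, "The subject has confirmed HBV virological breakthrough" (criterion 12).

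**The concern.** The 48-week denominator is formed after the outcome has begun to occur. A subject whose breakthrough is confirmed before Week 24 must stop JNJ-56136379, does not complete 24 weeks, and cannot enter the extension. That subject counts in the 24-week figure and is absent from the 48-week figure. Conversely, breakthroughs in the extension are absent from the 24-week figure.

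A reader will expect a proportion over 48 weeks to be at least as large as one over 24 weeks in the same arm. Here it can be smaller, because the two rows describe different sets of subjects. Comparing arms on the 48-week row compares subjects who were selected differently, according to how many failed early in each arm. Breakthrough also matters to how this trial is run: it led to the closure of Arm 1 and to the futility rule for Arm 6 (Protocol 1.3.4 and 6.2).

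**Working it through.** The documents state no expected breakthrough rate or power for this endpoint, so there is no plan figure to reproduce. The check uses direct proportions.

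**Notation for one arm**
- n: subjects treated
- a: subjects with breakthrough by Week 24
- x: other subjects who do not enter the extension
- b: extension subjects whose first breakthrough is in the extension

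**Formulas** (taking extension subjects as free of earlier breakthrough)
- SAP 24-week figure = a/n
- SAP 48-week figure = b/(n − a − x)
- All-subject proportion over the whole treatment phase = (a + b)/n

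**Inputs.** Protocol 1.3.4 reports 5 confirmed breakthroughs among 28 subjects on 75 mg monotherapy, plus 2 who met the threshold without confirmation. I use n = 28 with a = 5 or 7 only to set a realistic scale. The timing of those events relative to Week 24 is not given, so placing them all before Week 24 is an assumption. The documents give no values for x or b; these are also assumed.

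| a | x | b | SAP 24-week | SAP 48-week | All subjects |
|---|---|---|---|---|---|
| 5 | 0 | 1 | 5/28 = 17.9% | 1/23 = 4.3% | 6/28 = 21.4% |
| 5 | 3 | 2 | 5/28 = 17.9% | 2/20 = 10.0% | 7/28 = 25.0% |
| 5 | 0 | 4 | 5/28 = 17.9% | 4/23 = 17.4% | 9/28 = 32.1% |
| 7 | 0 | 2 | 7/28 = 25.0% | 2/21 = 9.5% | 9/28 = 32.1% |

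**When the order reverses.** The 48-week figure is below the 24-week figure when b/(n − a − x) < a/n. With n = 28 and a = 5, this holds for b up to 4 when x = 0, and for b up to 3 when x = 3 or 6. With n = 30 and a = 3, it holds for b up to 2 when x = 0 or 6, and up to 1 when x = 12. With n = 30 and a = 1, it holds only when b = 0 (x = 0, 6 or 12). The all-subject figure can never be below a/n.

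**Can an extension subject have an earlier breakthrough?** Yes, in two narrow ways.
1. The HBV DNA check is tied to Week 20. A rise first seen at Week 24 and confirmed at Week 28 can occur in a subject already extended.
2. SAP 5.1 imputes target not detected as 5 IU/mL. Two consecutive values of 51 IU/mL are then a rise of log10(51/5) = 1.009, which meets the breakthrough definition while staying below 200 IU/mL.

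The exclusion of early breakthroughs is therefore nearly complete, not absolute.

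**The case against.** The strongest reply is that the SAP already covers the endpoint elsewhere. The closing list in SAP 5.3, Secondary Analysis, includes a breakthrough proportion by treatment group over study treatment and follow-up, with no extension restriction. Efficacy uses the ITT population, on-treatment means the treatment phase, that phase includes the extension (SAP 2.3), and the coding is cumulative. SAP 5.3 also defines time to breakthrough for each subject, with censoring. A reader might infer from the split table that the SAP never analyses the protocol endpoint; these entries do not support so strong a reading. They do not settle the matter either. The listed proportion has no window or denominator of its own, depends on a definition built on split time frames, and adds follow-up, which is outside the endpoint. The time-to-event entry refers back to the same definition and censors within an unspecified defined time frame. The Secondary Analysis list names no estimate or table for it.

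A second reply is that the restriction is openly labelled and the same convention serves other Week 48 outcomes, in an exploratory study without formal testing. That is fair, and it limits the severity. But the label does not tell the reader that entry to the extension depends on the outcome itself.

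Third, a reader might infer that the distortion is worst in monotherapy. The documents do not support this: Arm 1 was stopped, with its subjects sent to follow-up Schedule 1, and Arm 6 receives NA from Week 24, or sooner if the futility rule is triggered. No breakthrough counts are given for combination arms.

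Finally, an all-subject proportion mixes 24 and 48 weeks at risk, so arms that extend more subjects have more time in which to record events. This stands, and the fix allows for it.

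**Conclusion.** The point holds in a limited form. The 48-week proportion in SAP 5.3 is conditional on entering the extension, a condition that removes almost all earlier breakthroughs. Neither tabulated figure equals the endpoint in Protocol 2.1, and the remaining SAP entries do not clearly supply it.

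In the illustration with 5 early events, 3 others not extended and 2 extension events among 28, the SAP would show 17.9% and 10.0%, against 25.0% for all subjects over their whole treatment. This rests on the assumed timing of the 5 events and on assumed extension counts. Two stronger inferences fail: that extension subjects can have had no earlier breakthrough, and that the 48-week figure must come out lower. The first has the exceptions shown above, and the second depends on the counts. As this is a descriptive secondary endpoint, the change should be made, but it does not bear on the primary analysis.

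**What to change.** In SAP 5.3, under Parameter Definitions, in the breakthrough tabulation and in the closing list of categorical endpoints, define the breakthrough proportion as any confirmed breakthrough from first dose to the end of the subject's treatment phase (initial plus extension), with all ITT subjects of the arm as denominator.

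Because subjects are at risk for 24 or 48 weeks, report this alongside the censored time-to-breakthrough estimate. State that its time frame is the whole treatment phase in all ITT subjects, and add it to the list of planned outputs.

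Keep the extension-only figure as a supplement, labelled as applying to subjects who entered the extension.

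The cost is SAP wording, one table denominator and one additional output from a variable already defined. No new data and no change to trial conduct are needed. The all-subject figure will be no lower than the 24-week figure and may look less favourable than the present 48-week row.

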### **5. EFFICACY EVALUATIONS**

Efficacy assessments will be performed at the planned time points indicated in section 2.3 above (see Appendix 4, 5 and 6) using the ITT population. All HBV virology (i.e. HBV DNA and RNA) and serology (i.e. HBsAG, HBeAg, HbcAg, Anti-HBs, Anti-HBe) available data will be analyzed by subject population, hepatitis B e antigen (HBeAg) status

---

and overall, treatment group, analysis phase, analysis period and follow-up type and at each analysis time point (when applicable). Placebo treatments can be pooled as ‘placebo’ over Parts A and B. The sections below describe the data handling rules used in the primary, secondary and exploratory analysis.

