### **5.1. Data handling rules**

Units as provided in the SAP will be used in the analyses if these are deviated from the units provided in the Study Data Tabulation Model (SDTM) data. The viral activity parameters (i.e. virology and serology parameters) will be analyzed using log10 transformation rounded to 2 decimal places.

Historical as actual data for viral activity parameters will be used in the analysis. In the case a diluted and a non-diluted sample are present for a parameter at any time point, only the diluted sample will be included in the analysis. Historical viral activity measurements will not be imputed. The actual measurements will be imputed as follows:

- **HBsAg** values were tested with an upper limit of quantification of 124925.00 IU/mL and a lower limit of quantification of 0.05 IU/mL. Samples for the determination of HBsAg were processed in real-time using an assay such as the ARCHITECT platform (Abbott Laboratories).
  - Values above the upper limit of quantification (124925.00 IU/mL), will be imputed by the value of round (ULOQ+(ULOQ/10)) IU/mL in the analysis.
  - Values below the lower limit of quantification (0.05 IU/mL) will be imputed by a rounded value of (LLOQ/2) IU/mL in the analysis.
  
- **HBeAg** values were tested with an upper limit of quantification of 1400.00 IU/mL and a lower limit of quantification of 0.11 IU/mL.
  - Values above the upper limit of quantification (1400.00 IU/mL), will be imputed by a value of round (ULOQ+(ULOQ/10)) IU/mL in the analysis.
  - Values below the lower limit of quantification (0.11 IU/mL) will be imputed by a rounded value of (LLOQ/2) IU/mL in the analysis.

---

- **HBcrAg** values were tested within a measurement range of 3.0 LogU/mL - 9.0 LogU/mL
  - Values below lower limit of quantification (<3.0 LogU/mL) will be imputed by 2.7 log U/mL
  - Values above the upper limit of quantification (official ULOQ = 7 Log U/ml but with dilution ULOQ= 9.0 Log U/ml) will be imputed by value of round (ULOQ+(ULOQ/10)) log10U/mL with or without dilution method
- **Plasma HBV DNA** values were measured by the HBV COBAS AmpliPrep – COBAS TaqMan, V. 2.0 test (lower limit of quantification 20 IU/mL). Values below the lower limit of quantification (20 IU/mL) will be imputed as follows:
  - Values below the lower limit of quantification (20 IU/mL), but target detected will be imputed by a value of 15 IU/mL in the analysis.

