  - Values below the lower limit of quantification (20 IU/mL, target not detected) will be imputed by a value of 5 IU/mL in the analysis.
  - Values above the upper limit of quantification (>170000000 IU/mL), will be imputed by the value of round (ULOQ+(ULOQ/10)) IU/mL in the analysis
- **HBV RNA** values were tested with an upper limit of quantification (ULOQ) and a lower limit of quantification (LLOQ), all values, even below LLOQ (4.0 log10 cp/mL) or LOD (2.49 log10 cp/mL) will be reported and all numeric values will be used in the analysis.
  - Negative or Not Detected (“TND”) values will be imputed by a value of 5 copies/mL ( $\log_{10}(5) = 0.69897$  log10 cp/mL) in the analysis.
  - Values above the upper limit of quantification (>ULOQ), will be imputed by the value of round (ULOQ+(ULOQ/10))  $\log_{10}$  cp/mL in the analysis
- **Anti-HBs** values were tested with an upper limit of quantification (ULOQ) and lower limit of quantification (LLOQ), all values, even below LLOQ (< 5.0 mIU/mL) will be reported and all numeric values will be used in the analysis.

---

- Values below LLOQ (<5mIU/mL) will be imputed by value of round (LLOQ/2) mIU/mL
- Values “>10000.00 mIU/mL” (with annotation “diluted for quantitation”) will be imputed by value of round (ULOQ+(ULOQ/10)) mIU/mL

Additionally, all other viral activity data with values below a LLOQ and not included in the imputation rules above will be imputed by the absolute value divided by 2 and rounded to the amount of decimal place provided in the dataset.

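### Imputed HBV DNA values of 5 or 15 IU/mL can set the breakthrough nadir, so the >1 log10 limb is met from 51 or 154 IU/mL and the >200 IU/mL limb becomes redundant after an on-treatment nadir below LLOQ

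*SAP*

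**What the plan says.** **Definition.** SAP Section 5.3, under Parameter Definitions (numbered 5.2.1 in the text), gives breakthrough two limbs joined by a plain *or*. The first is a confirmed rise of more than 1 "log10 from nadir level (lowest level reached during 24/48 weeks treatment". The second is a confirmed value above 200 IU/mL in a subject who had been below LLOQ. Confirmation needs two or more consecutive time points, or the last one on treatment. "On-treatment means in the treatment phase, except for the baseline record".

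**Data handling.** SAP Section 5 states: "The sections below describe the data handling rules used in the primary, secondary and exploratory analysis". Section 5.1 says that viral parameters "will be analyzed using log10 transformation rounded to 2 decimal places", and then: "The actual measurements will be imputed as follows". For HBV DNA the LLOQ is 20 IU/mL. A result below it "but target detected will be imputed by a value of 15 IU/mL in the analysis"; a target-not-detected result "will be imputed by a value of 5 IU/mL in the analysis".

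**Use.** The breakthrough proportion is a secondary endpoint in Protocol Section 2.1. In the SAP it enters on-treatment failure for the 24-week period ("Or for subject who experienced viral breakthrough as defined above"), the time-to-event analysis in Table 5, a dedicated listing in Section 5.3, and the sequencing time points and tables of Section 7.

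**Protocol.** The Synopsis, Section 2.1 and discontinuation criterion 12 in Section 10.2 carry the same two limbs. The Section 6.2 futility rule turns on the same event. The protocol has no imputation rule and does not say what value a result below LLOQ takes as a nadir.

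**The concern.** The constants 5 and 15 IU/mL let results below LLOQ enter continuous summaries. Because Section 5.1 covers secondary analyses and the breakthrough definition exempts nothing, the same constants become the nadir for any subject who goes below LLOQ on treatment. The log10 limb then starts well under 200 IU/mL, and the limb written for subjects who had been below LLOQ stops adding cases among them.

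A programmer who follows the text will count confirmed low-level values as breakthrough. Another, who reads the 200 IU/mL limb as the rule for such subjects, will not. The reported proportion would then depend on an imputation choice, and so would on-treatment failure, time to breakthrough and the choice of sequencing samples. Nadirs below LLOQ should be common in the virologically suppressed arms (about 40 planned subjects in each Part), who enter with HBV DNA below 60 IU/mL.

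**Working it through.** **Inputs.** LLOQ 20 IU/mL, imputed values 5 and 15 IU/mL, and two-decimal log10 (SAP Section 5.1); limbs >1 log10 and >200 IU/mL (SAP Section 5.3); planned arms of 30 and 10 (Protocol Section 3.1). I assume HBV DNA is reported in whole IU/mL.

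**Step 1: where the log10 limb starts.** Find the smallest v with round(log10 v, 2) − round(log10 nadir, 2) > 1. Without rounding the condition is v > 10 × nadir.

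| Nadir (IU/mL) | log10 | Last value not meeting the limb | First value meeting it | Unrounded |
|---|---|---|---|---|
| 5 | 0.70 | 50 (rise 1.00) | 51 (1.71 − 0.70 = 1.01) | 51 |
| 15 | 1.18 | 153 (rise 1.00) | 154 (2.19 − 1.18 = 1.01) | 151 |
| 20 (floor) | 1.30 | 201 (rise 1.00) | 202 (2.31 − 1.30 = 1.01) | 201 |

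In ordinary floating-point arithmetic 2.18 − 1.18 comes out slightly above 1, so simple code could also flag 153.

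**Step 2: does the 200 IU/mL limb add anyone?** At 201 IU/mL the rounded rise is already 2.30 − 0.70 = 1.60 from a nadir of 5, and 2.30 − 1.18 = 1.12 from 15. Every higher value also passes. With an on-treatment nadir below LLOQ, the second limb adds no case.

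**Step 3: values flagged by the log10 limb alone.** After target not detected: 51 to 200, which is 150 whole values. After target detected below LLOQ: 154 to 200, which is 47 whole values.

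**Step 4: an example.** A subject with target not detected, then 60 IU/mL at Weeks 16 and 20, has a rise of 1.78 − 0.70 = 1.08. The SAP counts a breakthrough and an on-treatment failure, while the Week 20 value still meets the <200 IU/mL extension criterion (Protocol Section 6.1, repeated in SAP Section 5.3).

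**Step 5: where the 200 IU/mL limb still matters.**
- *Below LLOQ at baseline only.* The baseline record is not on-treatment, so it cannot set the nadir. With an on-treatment nadir of 25, the log10 limb starts at 251 (unrounded). The second limb would add 201 to 250 if the baseline result counts as having been below LLOQ, which the SAP does not say.
- *First below LLOQ during NA follow-up.* The SAP also derives breakthrough in NA follow-up, but defines the nadir over the 24/48-week treatment. A monotherapy subject with a treatment nadir of 500, then below LLOQ on NA, then 300, meets only the second limb. All Arm 1 subjects were to start NA and enter follow-up, so this case is foreseeable.

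**Step 6: effect of one subject.** 1/30 = 3.3 points in a JNJ-56136379 arm; 1/10 = 10 points in a placebo+NA arm; 1/20 = 5 points when the two placebo+NA arms of one population are pooled.

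**The case against.** The strongest objection is that the two limbs are the protocol's own wording, shared with a discontinuation criterion and a futility rule. Settling the reading in the SAP alone could leave a subject who stopped JNJ-56136379 for breakthrough outside the breakthrough count. That stands, and it is why the passages need reconciling.

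A reader might infer that the log10 limb was meant only for quantifiable nadirs, with 200 IU/mL as the sole rule after a result below LLOQ. The figures invite this, since 10 × 20 = 200, but neither document says it or explains where 200 comes from. The Week 20 comparison is not proof either: that criterion governs extension and does not define breakthrough, so meeting both is not in itself a contradiction.

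A reader might also infer that the 200 IU/mL limb is overridden altogether. It is not. The limbs are alternatives, so it is redundant for on-treatment nadirs below LLOQ and can still act in the two situations in Step 5.

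Finally, the trial is exploratory with no formal hypothesis testing, the primary HBsAg analysis is untouched, and all individual values are listed and plotted. This limits the weight of the point. It does not supply a reproducible derivation for a secondary endpoint that will be reported.

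**Conclusion.** The concern holds for the analysis derivation. Read literally, SAP Sections 5.1 and 5.3 together let an imputation constant set the nadir. Breakthrough is then first met at 51 IU/mL (nadir 5) or 154 IU/mL (nadir 15; 151 unrounded), and the 200 IU/mL limb is redundant for those nadirs. This rests on applying Section 5.1 to the breakthrough derivation, as the SAP's scope sentence indicates, and on taking differences of rounded logs for the figure of 154.

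The number of subjects affected cannot be derived from the documents. Purely as an assumed range, 0 to 3 subjects in an arm of 30 would shift the proportion by 0 to 10 points (3/30). It would be wrong to infer that the 75 mg monotherapy breakthroughs reported in Protocol Section 1.3.4 (5 of 28 subjects) arose this way: their HBV DNA values are not given, and the protocol definition carries no imputation. The point should be fixed before the breakthrough tables are produced.

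**What to change.** For the analysis derivation only:

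1. State in SAP Section 5.3 that the 5 and 15 IU/mL imputations do not serve as the nadir for the >1 log10 limb. Flooring the nadir at 20 IU/mL is equivalent: the floored limb starts at 202 (201 unrounded) and the other limb already catches 201.
2. State how the nadir and the condition of having been below LLOQ are set when that happened only at baseline, and during NA follow-up.
3. Show the count with imputed nadirs as a sensitivity row, and list subjects whose status differs, including for the sequencing tables.
4. Reconcile SAP Sections 5.1 and 5.3 with the Protocol Synopsis and Sections 2.1, 6.2 and 10.2, so that a subject handled as a breakthrough in the trial is not silently dropped from the endpoint. No position is taken here on which threshold should govern discontinuation.

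The cost is a few SAP sentences, one programming change, a sensitivity row and a short listing. The downside is that confirmed rises to 51–200 IU/mL after a nadir below LLOQ leave the main breakthrough count, its listing and the breakthrough sequencing tables. SAP Table 4 has HBV DNA cut-offs at 100 and 1000 IU/mL but none at 200, so it does not isolate them. They would be seen only in the sensitivity row, the listing of differing subjects, and the full subject listings and plots.
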